2.3.2. INCB086550 Nonclinical Safety Summary

In vitro studies were conducted to characterize the potential risks of inhibiting the PD-(L)1 interaction with INCB086550. These studies demonstrated that INCB086550 binds to human PD-L1 and disrupts the PD-L1/PD-1 interaction at nanomolar concentrations. Clinical studies with blocking antibodies to either PD-1 or PD-L1 have shown an induction of autoimmune responses. Given the mechanism of action of INCB086550, autoimmune AEs may be seen upon administration. Nonclinical pharmacology and toxicology studies have shown no adverse effects or target organ toxicity.

In the pivotal 28-day studies, INCB086550 was well tolerated at all tested doses up to 1000 mg/kg in rats and 715 mg/kg per day in monkeys. Findings associated with INCB086550 in rats were observed only at 1000 mg/kg per day and included decreased red blood cell mass (red blood cells, hemoglobin, and hematocrit), higher reticulocyte counts and red cell distribution, higher neutrophil and monocyte counts, and histiocytic infiltrates in the duodenum, jejunum, and/or ileum, and increased apoptosis/necrosis in the ileum in both males and females. The severity of these findings was limited to minimal to mild, and they were thus considered nonadverse. Treatment-related findings in monkeys were limited to emesis at doses \geq 200 mg/kg per day with no evidence of target organ toxicity.

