6.5.1. Management of Immune-Related Adverse Events

An AE of a potential immunologic etiology or an irAE may be defined as an AE consistent with an immune phenomenon associated with drug exposure after all other etiologies have been eliminated. Immune-related AEs may be expected based on the nature of INCB086550, its mechanism of action, and reported experience with other immunotherapies. If an irAE is suspected, efforts should be made to rule out neoplastic, infectious, metabolic, autoimmune, toxic, or other etiologic causes before categorizing an AE as an irAE. The investigator should promptly notify the sponsor (or designee) about participants who develop an irAE \geq Grade 2.

Participants, who have irAEs that resolve to \leq Grade 1 within 14 days, may be rechallenged at the starting dose or with a dose reduction. Continuation, withholding, dose modification, or discontinuation of INCB086550 will depend on severity of the irAE and affected organ/organ system and should be discussed with the medical monitor. Any irAEs \geq Grade 3 that require permanent discontinuation of INCB086550 per [Table 10](#) may only be rechallenged with approval of the medical monitor. Elevations in amylase or lipase that are \geq Grade 3 do not require dose interruption or reduction if the participant is asymptomatic or if the elevation is clinically insignificant and has been discussed with the medical monitor.

Participants should receive appropriate supportive care measures as deemed necessary by the treating investigator. Suggested measures for the management of irAEs are outlined in [Table 10](#). For each AE, attempts should be made to rule out other causes, including but not limited to metastatic disease, bacterial infection, or viral infection that might require specific supportive care.

Management guidance for irAEs not detailed elsewhere in the Protocol should follow the ASCO Clinical Practice Guideline or ESMO Clinical Practice Guidelines ([Brahmer et al 2018](#), [Haanen et al 2017](#)).

Table 10: Immune-Related Adverse Events Management Guidelines for INCB086550

irAE	CTCAE v5 Grade	Guidance for Restarting INCB086550	Monitoring and/or Supportive Care

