	Grade 4	Permanently discontinue INCB086550.	
 Administer IV methylprednisolone 1-2 mg/kg or equivalent with taper. If no improvement after 2-3 days, consider infliximab 5-10 mg/kg. Gastroenterology consult for additional workup as appropriate.

Table 10: Immune-Related Adverse Events Management Guidelines for INCB086550 (Continued)

irAE	CTCAE v5 Grade	Guidance for Restarting INCB086550	Monitoring and/or Supportive Care
Hepatitis (AST/ALT increased and/or total bilirubin increased)	Grade 1	Continue INCB086550.	
 Repeat laboratory measurements 1-2 times/week until return to baseline. Provide supportive care for symptoms.
	Grade 2 or Grade 3 lasting \leq 10 days	Withhold INCB086550 until resolution to \leq Grade 1.	
 Repeat laboratory measurements every 3 days until return to baseline. If elevations persist after 3 days or symptomatic, administer systemic corticosteroids (prednisone 0.5-1 mg/kg or equivalent) with taper. Infliximab should NOT be used.
	Grade 3 lasting > 10 days or Grade 4	Permanently discontinue INCB086550.	
 Repeat laboratory measurements every 1-2 days until return to baseline. Administer IV methylprednisolone 1-2 mg/kg or equivalent with taper. If corticosteroid refractory or elevations persist after 3 days, consider mycophenolate mofetil or azathioprine. Infliximab should NOT be used. Hepatology consult for additional workup, as appropriate.
Dermatitis	Grade 1 or Grade 2	Continue INCB086550.	
 Consider dermatology consult. Supportive care with topical emollients, oral antihistamines. Administer topical corticosteroid as needed. If no improvement with topical corticosteroid, consider systemic (oral) corticosteroid.
	Grade 3	Withhold INCB086550 until resolution to \leq Grade 1.	
 Dermatology consult. Administer IV methylprednisolone 1-2 mg/kg or equivalent with taper.
	Grade 4	Permanently discontinue INCB086550.	
 Monitor for progression to severe cutaneous adverse reaction (eg, Stevens-Johnson syndrome, toxic epidermal necrolysis, drug reaction with eosinophilia and systemic symptoms/drug-induced hypersensitivity syndrome).
Nephritis or renal dysfunction (creatinine increased)	See Table 12 for immune-related nephritis and renal dysfunction AE management guidelines.		

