6.5.2. Criteria and Procedures for Dose Interruptions and Adjustments of Study Drug

Dose interruptions and modifications of INCB086550 may occur for participants during the study treatment period. The short half-life of INCB086550 (8.62 hours after a single 100 mg dose) may improve management options for participants who experience irAEs, unobtainable with immune checkpoint monoclonal antibodies, which possess long half-lives. Management guidelines for AEs requiring dose modifications are described for general hematologic and nonhematologic toxicities that are not thought to be immune-related in [Table 11](#). Decisions regarding dose interruptions of INCB086550 should be made using clinical judgment of the investigator, taking into account the possible relatedness of the AE to the study drug and the participant's underlying condition. Adverse events that have a clear alternative explanation or transient (≤ 72 hours) abnormal laboratory values without associated clinically significant signs or symptoms may be exempt from dose-interruption/discontinuation rules. Participants may resume treatment as per management guidelines if no medical condition or other circumstance exists that, in the opinion of the investigator, would make the participant unsuitable for further treatment and participation in the study. Treatment with INCB086550 may be delayed for up to 28 days to allow for resolution of toxicity. The treating investigator should contact the medical monitor to discuss the case of any participant whose treatment has been interrupted for more than 28 days before restarting treatment with INCB086550.

Dose interruptions are permitted in the case of medical/surgical events or logistical reasons not related to study therapy (eg, elective surgery, unrelated medical events, subject vacation, holidays). Participants should be placed back on study therapy within 4 weeks (ie, 28 days) of the scheduled interruption, unless otherwise discussed with the medical monitor. The reason for interruption should be documented accordingly.

Safety concerns should be discussed with the sponsor immediately upon occurrence or awareness to determine if the participant should continue or discontinue study treatment. Additional unscheduled visits with CBC may be performed.

Table 11: Non-Immune-Related Adverse Events Dose Modification Guidelines

CTCAE Severity	Suggested Modification
Hematological toxicities	

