- Perform follow-up on subsequent laboratory results according to the guidance provided in Section 8.3.6.

Potential Hy's Law Criteria Met

If the participant has had AST or ALT $\geq 3 \times$ ULN AND total bilirubin $> 2 \times$ ULN at any point in the study (the elevations do not have to be at the same time or within a specified timeframe), irrespective of ALP, please follow the instruction below:

- Have participant interrupt study drug.
- Notify Incyte study team without delay.
 - The investigator, or designee, should contact the medical monitor to discuss and agree upon an approach for the study participant's follow-up and the continuous review of data.
- Monitor the participant until liver biochemistry parameters and appropriate clinical symptoms and signs return to normal or baseline levels, or as medically indicated.
- Investigate the etiology of the event and perform any relevant diagnostic investigations as discussed with the medical monitor.
- Enter the laboratory data into the laboratory CRF as soon as possible.
- If at any time (in consultation with the medical monitor) the PHL case meets serious criteria, report it as an SAE using standard reporting procedures.

REVIEW AND ASSESSMENT

No later than 3 weeks after the biochemistry abnormality is initially detected and the criteria for PHL is met, the medical monitor, Incyte pharmacovigilance physician, and investigator will discuss and review available data and agree on whether there is an alternative explanation for the elevations in liver biochemistry other than drug-induced liver injury caused by the study drug. Participant matter experts will be included in the review as appropriate.

Evaluation of Alternative Causes

In order to gather additional clinical information to seek other possible causes of the observed liver test abnormalities, the following alternative etiologies should be considered, including but not limited to,

- Active viral hepatitis
- Alcoholic and autoimmune hepatitis
- Hepatobiliary disorders
 - Biliary tract disease, such as migration of gallstones or intrahepatic lesions, more often causes cholestatic injury initially and should be investigated with gall bladder and ductal imaging studies, especially if alkaline phosphatase is increased. Malignant interruption of the biliary tract also should be considered.
- Concomitant treatment

- Other causes such as systemic infections (bacterial, fungal, viral), nonalcoholic steatohepatitis, and cardiovascular diseases

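### For immune-related hepatitis that meets Hy's law, Table 10 allows restart while Appendix D requires a permanent stop, and no sentence says which rule prevails

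*Protocol*

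**What the plan says.** **Expected toxicity.** Protocol section 2.3.2 states: "Given the mechanism of action of INCB086550, autoimmune AEs may be seen upon administration". Table 10 in section 6.5.1 has a row for "Hepatitis (AST/ALT increased and/or total bilirubin increased", so it covers either abnormality or both together.

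**Table 10 and section 6.5.1.** For hepatitis of Grade 2, or Grade 3 lasting no more than 10 days, study drug is withheld until the event is Grade 1 or lower. Permanent discontinuation applies to Grade 3 lasting more than 10 days and to Grade 4. Section 6.5.1 adds that participants whose immune-related events reach Grade 1 or lower within 14 days "may be rechallenged at the starting dose or with a dose reduction". Events of Grade 3 or above that Table 10 would stop permanently "may only be rechallenged with approval of the medical monitor".

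**Appendix D.** Study drug is interrupted when potential Hy's law criteria are met. The medical monitor, the sponsor's pharmacovigilance physician and the investigator then decide whether there is an "alternative explanation for the elevations in liver biochemistry other than drug-induced liver injury caused by the study drug". The causes to consider include "Alcoholic and autoimmune hepatitis". If an alternative explanation is agreed, drug may resume under the protocol's guidelines. If none is agreed, drug stops permanently and a serious adverse event is reported as related. No exception is made for immune-related cases.

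**Table 11 and related sections.** The table is titled "Table 11: Non-Immune-Related Adverse Events Dose Modification Guidelines", and section 6.5.2 limits it to toxicities not considered immune-related. Its all-grades row sends immune-related events to Table 10. The same row orders a permanent stop for any liver abnormality meeting Hy's law. Section 6.5.3 names Tables 10 and 11 together as the source of discontinuation criteria. Section 7.1.1 makes discontinuation mandatory for unacceptable toxicity as defined in 6.5.3. Section 9.3 refers potential Hy's law cases to Appendix D.

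**The concern.** An investigator managing immune-related hepatitis would naturally open Table 10, where the hepatitis row mentions neither Hy's law nor Appendix D. Followed as written, that row could lead to re-exposure after a liver injury that Appendix D says must end treatment. Hepatitis is a listed immune-related event for this drug, so the overlap is foreseeable.

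This is a participant-safety rule, not an analysis choice. ORR, DCR and DOR do not depend on it. The liver-injury listing in SAP section 9.3.3 is defined by laboratory values and their timing, so it does not depend on attribution either.

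**Working it through.** No sample size, power or error-rate figure bears on this point. The check sets the rules side by side.

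**Step 1: can one case meet both definitions?** Section 6.5.1 treats an immune-related event as a drug-associated immune phenomenon that remains after other causes are eliminated. Appendix D defines Hy's law as AST or ALT at least 3 × ULN with total bilirubin above 2 × ULN and no other reason for the combination. Hepatitis that passes the first test and has those laboratory values also passes the second.

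**Step 2: what does each text order for study drug?**

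| Text | Drug-caused, immune-related, meets Hy's law | Drug-caused, not immune-related, meets Hy's law |
|---|---|---|
| Table 10, hepatitis row | Restart at Grade 1 or lower, after Grade 2 or after Grade 3 lasting at most 10 days | Does not apply |
| Section 6.5.1, 14-day provision | Rechallenge permitted | Does not apply |
| Table 11, all-grades row | Permanent stop for any Hy's law abnormality, but the table is scoped to non-immune events and points to Table 10 | Permanent stop |
| Appendix D | Permanent stop | Permanent stop |

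The right-hand column is consistent. The conflict lies only in the left-hand column, and within it only in the grades and durations for which Table 10 allows restart. For Grade 4, or Grade 3 beyond 10 days, Table 10 and Appendix D both say stop.

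**Step 3: does any text set precedence?**

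- Section 6.5.3 names Tables 10 and 11 without ranking them and does not name Appendix D.
- Section 7.1.1 makes the 6.5.3 criteria mandatory. The route to a Hy's law stop therefore runs through Table 11, whose scope is the point in doubt.
- Section 9.3 sends potential cases to Appendix D but does not say that Table 10 gives way.
- Appendix D has no immune exception and does not mention Table 10.

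The balance favours the stop, but this has to be inferred.

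**Step 4: how many cases?** This cannot be computed. The overlap requires some cases at Hy's law levels to grade as 2, or as 3 for at most 10 days. The documents do not print the CTCAE v5 liver limits and give no rate for such events.

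**The case against.** The strongest reply is that the protocol, read as a whole, already requires the stop. Appendix D is the specific procedure for these cases, section 9.3 points to it, Table 11 says any liver abnormality, and sections 6.5.3 and 7.1.1 make discontinuation mandatory. The 14-day provision in 6.5.1 is permissive. The route needing medical monitor approval covers only discontinuations required by Table 10, so it does not by its terms lift a stop ordered elsewhere. Drug is interrupted in every potential case, three parties review it, and immune-related dosing is to be discussed with the medical monitor. Most of this stands, and it is why the point is minor. It does not close the gap. Table 11's title and its pointer to Table 10 give a fair reason to think its Hy's law line does not reach immune-related hepatitis, and the safeguards bring people together without telling them which rule to apply.

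Three stronger readings are tempting, but the documents do not support them.

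- *A reader might infer that all drug-caused Hy's law cases are unresolved.* They are not. For non-immune injury, Table 11 and Appendix D agree on a permanent stop.
- *A reader might infer that listing "Alcoholic and autoimmune hepatitis" lets drug-caused immune hepatitis count as an alternative explanation.* Appendix D's own test asks for a cause other than study-drug injury. Section 6.5.1 lists autoimmune causes among those to rule out before an event is called immune-related. The word is loose, because section 2.3.2 uses it for drug effects, but the context largely settles the meaning.
- *A reader might set the 14-day provision against the 3-week review and infer that restart is allowed 7 days (21 − 14) before review.* The review is due "No later than 3 weeks after the biochemistry abnormality is initially detected", which is a latest date. The 14 days is a resolution window with no stated start. Appendix D mentions resumption only among the actions after review. The subtraction shows no conflict.

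**Conclusion.** The concern holds for one subset: immune-related hepatitis attributed to INCB086550 that meets Hy's law and falls in the grades and durations for which Table 10 permits restart. For those participants the protocol gives opposite dosing instructions. Several sections lean towards the permanent stop, but none states that it overrides Table 10.

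Severity is minor. The conclusion assumes that some cases at Hy's law levels grade as 2 or as short-lived Grade 3, which the documents neither confirm nor exclude. The effect is on dosing after a serious liver injury, and no efficacy endpoint changes. Reach in this study is small, since SAP section 11.2.1 reports early termination with minimal enrollment. The point matters mainly if the text is used again.

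**What to change.** Add the following to the Table 10 hepatitis row and to Appendix D:

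*If potential Hy's law criteria are met, hold study drug until the Appendix D review is complete; if the case is agreed to be Hy's law, including immune-related hepatitis attributed to INCB086550, the permanent stop overrides the Table 10 restart rule and the Section 6.5.1 rechallenge options.*

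As an optional clarification, reword the autoimmune part of the Appendix D bullet to *autoimmune hepatitis not attributable to study drug*.

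The change needs no new procedure, assessment or analysis. Its cost is that some participants who could have restarted under Table 10 will be stopped permanently. How many cannot be estimated from the documents.

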APPENDIX E. CYTOCHROME P450 INHIBITORS/INDUCERS

Concomitant treatment with moderate and potent CYP3A4/CYP3A5 inhibitors or inducers are prohibited in this study.

Below is a list of potent and moderate inhibitors and inducers. This list is not exhaustive. For a comprehensive list, please check with your pharmacy personnel for the most current list of potent CYP3A4/CYP3A5 inhibitors or inducers.

Additional references include:

- Food and Drug Administration. Drug Development and Drug Interactions: Table of Substrates, Inhibitors and Inducers.
- EMA (2013) Guideline on the Investigation of Drug Interactions.
- NPS Australia.

Potent and Moderate CYP3A4/CYP3A5 Inhibitors

Aprepitant	Grapefruit	Posaconazole
Atazanavir	Grapefruit juice	Ritonavir
Cannabidiol (CBD)	Indinavir	Saquinavir
Casopitant	Itraconazole	Telithromycin
Clarithromycin	Ketoconazole ^a	Troleandomycin
Diltiazem	Mibepradil	Verapamil
Erythromycin	Nefazodone	Voriconazole
Fluconazole	Nelfinavir	

^a Note topical use of 2% ketoconazole cream is allowed.

Potent CYP3A4/CYP3A5 Inducers

Apalutamide	Enzalutamide	Phenytoin
Bosentan	Etravirine	Primidone
Carbamazepine	Mitotane	Rifampicin
Efavirenz	Phenobarbital	St. John's wort

APPENDIX F. COVID-19 PANDEMIC MITIGATION STRATEGIES AND INSTRUCTIONS

The COVID-19 global pandemic presents challenges to the ongoing conduct of clinical trials. In line with regulatory guidance regarding clinical trial execution during the pandemic, the sponsor has issued the following Protocol considerations to ensure participant safety is maintained and adequate benefit/risk analyses are applied relative to the completion of study procedures and maintaining the investigational product supply chain. Recognizing the dynamic nature and flexibility required to manage the impact of the pandemic on this clinical trial, additional details will be incorporated into respective study manuals and site-specific monitoring plans as applicable, with institutional requirements as warranted, and communicated to the investigative sites as needed. Relevant test results will be documented in the eCRF, and applicable changes to the ICF will be made and monitored.

Study Site Visits

If local travel restrictions, isolation requirements, or the investigator's benefit/risk assessment determines it to be unsafe for participants to attend study visits at the investigational site, the site staff may elect to pursue the following:

- In order to minimize participant risk, study visits may be conducted via telemedicine modalities (phone or video) or as per site institutional guidelines. At a minimum, a review of AEs and concomitant medications must be completed. On-site visits should be conducted whenever feasible and are required for administration of study treatment. The participant may also be asked to undergo additional safety laboratory assessments.
- In order to support investigator oversight of participant safety and disease management, the participant may be asked to undergo some laboratory tests or study procedures at a local laboratory or facility closer to the participant's residence rather than at the investigational site. In this case, the study physician will provide the participant with the list of parameters to be checked. These tests should be performed in certified laboratories.
- Some tests, such as ECG or CT scan assessments, may require longer windows due to the COVID-19 pandemic and may be performed outside the regularly scheduled visit window or may be conducted at the next scheduled visit. It is the investigator's responsibility to check with the facility (if performed at a different facility) that the data will be obtained and available for evaluation. General procedures performed outside of protocol parameters will be captured as protocol deviations due to COVID-19 in the eCRF.

Participant SARS-CoV-2 Infection and Study Treatment

An event of active SARS-CoV-2 infection by a participant in the study should be reported as an AE or SAE and appropriate medical intervention provided. For participants with active SARS-CoV-2 infection, study treatment should be delayed until the resolution of symptoms and until it is allowable for the participant to return to the clinic per institutional guidelines. Prior to restarting treatment, the participant should be afebrile for 72 hours and the treating physician should determine that the participant's condition is stable enough to resume study treatment. The

study physician should also consider if the participant is SARS-CoV-2 negative (by test) before restarting study treatment if COVID-19 was diagnosed during the trial. The study team should be notified when the study treatment is restarted. Safety monitoring following COVID-19 should be implemented as per institutional guidance or clinical judgment (eg, coagulation factors).

COVID-19 Vaccination

Participants may receive the COVID-19 vaccine as long as it is not a live vaccine, which is prohibited per the Protocol (see Section 5.2). COVID-19 vaccination will be captured in the eCRF as a concomitant medication. Administration of study treatment may be delayed to ensure vaccination is completed. The medical monitor may be consulted if needed.

Clinical Trial Monitoring

Study monitoring visits could be postponed; however, the site monitor and sponsor will continue to employ off-site monitoring practices such as routine communication methods (eg, phone calls, emails, video visits) with the sites to get information on trial progress, participant status, and information on issue resolution. The study monitor may remotely review data entered into the EDC for accuracy and completeness if allowed by the national regulatory body, investigational site, and/or in compliance with local authorities.

Reimbursement of Additional Expenses

The sponsor will reimburse for any extraordinary expenses, keeping appropriate documentation as evidence (eg, travel expenses for the local laboratory visit[s], the costs of local [proximate] laboratory tests).

